Given the novelty of SARS-CoV-2, its rapid spread among humans and its associated morbidity and mortality, there has been an explosion of epidemiological, clinical, virologic, and other scientific data regarding the propagation of effects of this virus emerging from China, the United States, and many other countries. These data have established that 1) SARS-CoV-2 is transmitted person-to-person [17], even from those who are asymptomatic or presymptomatic [18-20], 2) the virus is very infectious, with estimates of the R_0 (Reproductive number) ranging from 1.50 to 6.49, with a mean average of 3.28 and a median average of 2.79 [21], 3) the constellation of symptoms, signs, and an incubation period ranging between 2 and 14 days [22], and 4) the asymptomatic proportion of those infected being substantial, perhaps as high as 80% [17, 23-25]. Further, research has found that the risk of death from COVID-19 increases with age and with serious, comorbid conditions including hypertension, diabetes, cardiovascular disease, obesity, etc.

Finally, although much has been learned very quickly about SARS-CoV-2 and COVID-19, much more is still to be determined. The aforementioned CFR and similar estimates are from crude analyses that have only accounted for moderate to serious cases. Therefore, the true CFR is likely significantly lower. Further, the infection-fatality ratio (IFR), which is the proportion who die among all those infected regardless of any symptomology, is likely still even lower than the CFR, but both the CFR and IFR will not be known with certainty until well-designed and controlled seroepidemiology surveys have been conducted using well-validated antibody assays and thorough questionnaires to obtain symptom history. Also, the presence of natural immunity of those infected who survive and the durability of such natural immunity is to be determined. Thus, the existence and possibility of reinfection and recurrent infection is unknown.

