3.7 EFFICACY ASSESSMENT (PHASE 3 SEGMENT ONLY)

Subjects will receive either active investigational product (INO-4800, dose selected from the Phase 2 segment) or placebo (placebo for INO-4800) in a 2-dose regimen administered intradermally followed immediately by EP on Days 0 and 28. Subjects will be monitored through regularly scheduled clinic visits and phone calls throughout the trial. Subjects will be regularly tested for SARS-CoV-2 infection using serologic testing. If COVID-19 disease is suspected based on symptoms or laboratory testing, site personnel will arrange for a clinic visit. Subjects with symptom(s) or a positive SARS-CoV-2 test result will be reviewed by the independent blinded EAC.

The mechanism for review and confirmation of cases will be outlined in an EAC Charter.

3.7.1 CASE DEFINITION FOR VIROLOGICALLY-CONFIRMED COVID-19 DISEASE:

- Positive testing by SARS-CoV-2 RT-PCR assay (performed at central lab*) with fever (temperature of 100.4°F/38.0°C or higher), or
- Positive testing by SARS-CoV-2 RT-PCR assay (performed at central lab*) with any of the following COVID-19 related symptoms:
 - Feeling feverish or chills
 - Cough
 - Shortness of breath or difficulty breathing
 - Fatigue
 - Muscle or body aches
 - Headache
 - New loss of taste or smell
 - Sore throat
 - Congestion or runny nose
 - Nausea or vomiting
 - Diarrhea

*Local lab results will be accepted if the subject is hospitalized and a sample is not able to be obtained for analysis at central lab.

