3.7.2 CASE DEFINITION FOR SARS-COV-2 ASYMPTOMATIC INFECTION

Positive testing by SARS-CoV-2 serologic assay (performed at central lab);

• Without clinical signs or symptoms of COVID-19 disease since the previous negative serologic test.

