8.5.1 PRIMARY ANALYSIS

Phase 2 Segment

Post-baseline increases from baseline in interferon-γ ELISpot response magnitudes will be compared between treatment groups using differences in medians and associated non-parametric 95% CIs.

INO-4800	COVID19-311
Inovio Pharmaceuticals, Inc.	Clinical Protocol

Post-baseline increases from baseline in neutralizing antibody response titers will be compared between treatment groups using ratios of geometric mean fold-rises and associated t-distribution based 95% CIs.

The summaries listed above will be stratified according to NP positive/negative status and according to prior receipt of any non-study prophylactic COVID-19 vaccine of the subjects. Valid samples for statistical analysis purposes will be those collected: at least 6 and no more than 30 days after Dose 2 for the Week 6 timepoint; at least 174 and no more than 198 days after Dose 2 for the Week 30 timepoint; and at least 356 and no more than 380 days after Dose 2 for the Week 56 timepoint. Baseline is defined as the last measurement prior to the first treatment administration.

The PP population will be used for these immunogenicity analyses.

Phase 3 Segment

Among subjects who are SARS-CoV-2 seronegative at baseline, the primary hypothesis of relative efficacy greater than 30% will be tested with H_0 : $p \ge 0.70/(0.70+k)$ vs. H_1 : p < 0.70/(0.70+k), where p is the true proportion of subjects with disease who receive INO-4800 relative to the total number of subjects with disease, and k is the total amount of follow-up time in the placebo group divided by the total amount of follow-up time in the INO-4800 group.

A p-value for this hypothesis test and corresponding confidence interval will be computed based on the exact binomial method of Clopper-Pearson. Success will be concluded if the one-sided p-value is <0.022 and the corresponding lower bound of the two-sided 95.6% Cl for efficacy exceeds 30% (alpha-level adjusted for interim analyses, see Section 8.5.6), and the point estimate for efficacy exceeds 50%.

For calculating k, an individual subject's follow-up time is either:

- the date of first disease diagnosis date of the start of surveillance period +1 (for subjects who are cases), or
- the date of last follow-up date of the start of surveillance period +1 (for subjects who are non-cases).

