8.5.2.2 Immunogenicity

Phase 3 Segment

Post-baseline increases from baseline in interferon- γ ELISpot response magnitudes will be compared between treatment groups using differences in medians and associated non-parametric 95% CIs.

Post-baseline increases from baseline in neutralizing antibody response titers will be compared between treatment groups using ratios of geometric mean fold-rises and associated t-distribution based 95% CIs.

The summaries listed above will be stratified according to disease status of the subjects and by baseline SARS-CoV-2 serostatus.

Valid samples for statistical analysis purposes will be those collected: at least 6 and no more than 30 days after Dose 2 for the Week 6 timepoint; at least 174 and no more than 198 days after Dose 2 for the Week 30 timepoint; and at least 356 and no more than 380 days after Dose 2 for the Week 56 timepoint. Baseline is defined as the last measurement prior to the first treatment administration.

The PP population will be used for these immunogenicity analyses.

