8.5.9.2 Immunogenicity

Phase 2 segment

Post-baseline increases from baseline in cellular response magnitudes will be compared between treatment groups using differences in medians and associated non-parametric 95% CIs.

The summaries listed above will be stratified according to NP positive/negative status and according to prior receipt of any non-study prophylactic COVID-19 vaccine of the subjects.

Valid samples for statistical analysis purposes will be those collected: at least 6 and no more than 30 days after Dose 2 for the Week 6 timepoint; at least 174 and no more than 198 days after Dose 2 for the Week 30 timepoint; and at least 356 and no more than 380 days after Dose 2 for the Week 56 timepoint. Baseline is defined as the last measurement prior to the first treatment administration.

The PP population will be used for immunogenicity analyses.

Phase 3 Segment

Post-baseline increases in antibody titers from ELISA will be compared between treatment groups using ratios of geometric mean fold-rises and associated 95% t-distribution based CIs.

Post-baseline increases from baseline in cellular response magnitudes will be compared between treatment groups using differences in medians and associated non-parametric 95% CIs.

Post-baseline increases from baseline in neutralizing antibody response titers will be compared between treatment groups using ratios of geometric mean fold-rises and associated t-distribution based 95% CIs.

The summaries listed above will be stratified according to disease status of the subjects.

Valid samples for statistical analysis purposes will be those collected: at least 6 and no more than 30 days after Dose 2 for the Week 6 timepoint; at least 174 and no more than 198 days after Dose 2 for the Week 30 timepoint; and at least 356 and no more than 380 days after Dose 2 for the Week 56 timepoint. Baseline is defined as the last measurement prior to the first treatment administration.

The PP population will be used for immunogenicity analyses.

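### Phase 3 immunogenicity summaries separate subjects by symptomatic disease only, so antibody raised by asymptomatic infection after baseline is counted as vaccine or placebo response, mainly at Weeks 30 and 56

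*Protocol*

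**What the plan says.** Section 8.1 states that the formal statistical analysis plan is Section 8 itself, so the strata named there are the plan.

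- **Phase 3 secondary immunogenicity (8.5.2.2; neutralizing antibody and ELISpot):** "The summaries listed above will be stratified according to disease status of the subjects and by baseline SARS-CoV-2 serostatus".
- **Phase 3 exploratory immunogenicity (8.5.9.2; binding antibody, neutralizing antibody, cellular response):** "The summaries listed above will be stratified according to disease status of the subjects". Baseline serostatus is not mentioned. The persistence endpoints in Table 8 (binding and neutralizing antibody from Week 30 on) fall here.
- **Phase 2 (8.5.1):** "The summaries listed above will be stratified according to NP positive/negative status", with NP given as nucleocapsid protein in the abbreviation list. The visit at which NP status is read is not stated.
- **Disease (3.7.1):** positive RT-PCR with fever, or "Positive testing by SARS-CoV-2 RT-PCR assay (performed at central lab*) with any of the following COVID-19 related symptoms".
- **Asymptomatic infection (3.7.2), a separate category:** a positive serologic result "Without clinical signs or symptoms of COVID-19 disease since the previous negative serologic test".

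The immunogenicity population is per-protocol (8.4): all doses received and no protocol violations. Infection is not a reason for exclusion. Section 6.4.8 and Table 4 provide Phase 3 SARS-CoV-2 serology at each scheduled clinic visit, to find infections whether or not symptoms occur.

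**The concern.** A fold-rise from baseline measures vaccine response only in subjects whose antibody was not raised by something else. Phase 3 recruits people at high risk of exposure and follows them for 56 weeks, so infection after baseline is expected. The protocol's own background calls "the asymptomatic proportion of those infected being substantial, perhaps as high as 80" per cent.

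Splitting by disease status removes infections that caused confirmed illness. Splitting by baseline serostatus removes infections before Day 0. Neither removes an asymptomatic infection between Day 0 and the sampling visit. Such subjects sit with the non-diseased: in the placebo arm they create a response where none is expected, and in the vaccine arm they can mask waning. The estimates at stake are the Week 30 and Week 56 fold-rises, which carry the persistence objective, and the vaccine-to-placebo ratio at those visits.

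**Working it through.** **The plan's own figure.** Placebo cases 2238 × 0.037 = 82.8; vaccine cases at 60% efficacy 4476 × 0.037 × 0.40 = 66.2; total 149.05. This reproduces the 149 cases and shows that 3.7% is the placebo attack rate of symptomatic disease over the efficacy window.

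**Inputs.** Attack rate 0.037 (8.6). Asymptomatic share of infections *s*: 0.80 is the background section's upper figure; the lower values are assumptions. Fold-rise after infection *F*: not in the document. I use 4.3, the Week 6 neutralizing rise of the 2.0 mg arm in 1.3.7.2, purely as a scale. Placebo GMFR without infection: 1.0 (assumed). About 204 subjects have both humoral and cellular analysis (6.5: 102 per age group), hence about 68 on placebo at 2:1.

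**Formulas.** Asymptomatically infected placebo share by end of study: a = 0.037 × s/(1 − s). Placebo GMFR = F^a. For Week 30, scale a by (210 − 42)/(393 − 42) = 168/351 = 0.479, assuming a constant hazard.

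| s | a | of 68 placebo | GMFR Week 56 | GMFR Week 30 |
|---|---|---|---|---|
| 0.20 | 0.9% | 0.6 | 1.01 | 1.01 |
| 0.40 | 2.5% | 1.7 | 1.04 | 1.02 |
| 0.60 | 5.6% | 3.8 | 1.08 | 1.04 |
| 0.80 | 14.8% | 10.1 | 1.24 | 1.11 |

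Dividing a by the non-diseased fraction (0.148/0.963 = 0.154) changes the top Week 56 value only from 1.24 to 1.25.

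**Week 6.** Even if the same hazard ran from Day 0, a is at most 0.148 × 42/351 = 0.018, and 4.3^0.018 = 1.03.

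**Sensitivity to F.** At s = 0.80 and Week 56, placebo GMFR is 1.23 for F = 4, 1.41 for F = 10 and 1.78 for F = 50. At s = 0.20 it is 1.01 to 1.04 over the same range.

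**Vaccine-to-placebo ratio** (true value set to 4.3, F = 4.3, s = 0.80, Week 56):
- Infection multiplies the titre equally in both arms and the vaccine does not prevent asymptomatic infection: ratio unchanged at 4.3.
- Infection multiplies the titre and the vaccine prevents 60% of asymptomatic infections: 4.3 × 4.3^(0.0592 − 0.148) = 3.8.
- Infected vaccinees end no higher than their vaccine response: 4.3/1.24 = 3.5.

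**ELISpot.** The comparison is of medians. If all 14.8% lie above the median, the placebo median moves to the 0.50/0.852 = 59th percentile of the uninfected distribution; at 0.9% it moves to 0.50/0.991, between the 50th and 51st.

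**The case against.** The strongest reply is that these endpoints are secondary or exploratory, carry no formal hypothesis, and may be affected very little. Much of that stands. At a 20% share the inflation is about 1%. Week 6, where the main response is read, is nearly clean. Titres after infection may fall: the background reports declining IgG in 93.3% of asymptomatic subjects in early convalescence, which would reduce carry-over to later visits. ELISpot medians are robust to this.

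Two further limits stand. The Phase 2 comparison shows that the sponsor recognises NP status as a useful split, but 8.5.1 gives no timing for it and Table 3 lists serology only at Screening, so Phase 2 is not a template for infection status up to a visit. Also, the Phase 3 wording shown is that of versions 1.0USA and 2.0USA; of version 7.0 only the end of the reference list is visible, so its wording cannot be checked.

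A reader might also infer that vaccinees will be misread as infected, and unblinded when notified, because 3.7.2 requires only "Positive testing by SARS-CoV-2 serologic assay (performed at central lab") and names no antigen. The document does not support this. Nothing says that the assay detects spike antibody, and 6.4.8 gives its purpose as finding infections after dosing, which implies an assay that can tell infection from vaccination.

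None of this answers the central observation: under the written strata, asymptomatic infection after baseline is set aside nowhere.

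**Conclusion.** The point holds as a modest, cheaply corrected weakness in the Phase 3 secondary and exploratory immunogenicity summaries. As written, asymptomatic infection after baseline is counted as response to the assigned arm. For neutralizing antibody the non-diseased placebo GMFR is inflated by about 1–24% at Week 56, about 1–11% at Week 30 and negligibly at Week 6. These figures rest on the planned 3.7% attack rate, an assumed asymptomatic share of 20–80%, an assumed 4.3-fold rise, a constant hazard and no waning.

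Stronger readings do not follow. Inflation of up to 60% could be obtained by raising the 23.5-fold vaccine-induced binding rise to the power 0.148. That figure comes from a different assay than those in 8.5.2.2, is not an infection response, and says nothing about medians. Nor is the ratio always biased: it is usually pulled towards 1, but is unchanged if infection acts equally in both arms. The primary efficacy analysis is not affected.

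**What to change.** In 8.5.2.2 and 8.5.9.2, keep the planned summaries and add beside them a summary by evidence of SARS-CoV-2 infection between baseline and the sampling visit. Define evidence as any positive RT-PCR or anti-nucleocapsid seropositivity in that interval, with or without symptoms. Using any positive result up to the visit, rather than status at the visit, guards against antibody that has since declined. In 8.5.9.2 also add the split by baseline serostatus that 8.5.2.2 already has.

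The cost is a wording change and one more set of tables; Table 4 already schedules the serology and no visit is added. The sponsor should confirm that the serology in use reads nucleocapsid. The drawback is that infection-free subjects are selected after randomisation, on an outcome the vaccine may influence. Their summary therefore supplements the planned one and does not replace it.

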8.5.3 SAFETY ANALYSES

8.5.3.1 Adverse Events

All AEs including injection-site reactions will be summarized among the Safety Population by frequency per treatment arm. These frequencies will be presented overall and separately by dose, and will depict overall, by system organ class and by preferred term, the percentage of subjects affected. Additional frequencies will be presented with respect to maximum severity and to strongest relationship to Study Treatment. Multiple occurrences of the same AE will be counted only once following a worst-case approach with respect to severity and relationship to Study Treatment. All serious AEs will also be summarized as above.

The main summary of safety data will be based on events occurring within 30 days of any dose. For this summary, the frequency of preferred term events will be compared between study arms with risk differences and 95% confidence intervals, using the method of Miettinen and Nurminen. As this analysis will use many event categories, and produce many confidence intervals, caution should be exercised when interpreting these confidence intervals. Separate summaries will be based on events occurring within 7 days of any dose and regardless of when they occurred.

The analyses listed above will be performed according to the Phase of the trial. For the Phase 2 segment, the analyses listed above will also be performed according to prior receipt of any non-study prophylactic COVID-19 vaccine. For the Phase 3 segment, the analyses listed above will also be performed according to SARS-CoV-2 serostatus at baseline.

For AE data, partial start dates will be imputed to the date of treatment to conservatively report the event as treatment-emergent, whenever the portion of the date is consistent

INO-4800	COVID19-311
Inovio Pharmaceuticals, Inc.	Clinical Protocol

with that of the study treatment. Otherwise, it will be imputed to the earliest date consistent with the partial date. A completely missing onset date will be imputed as the day of treatment. Partial stop dates will be assumed to be the latest possible day consistent with the partial date. AE duration will be calculated as (Stop Date – Start Date) + 1.

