3.0 CLINICAL TRIAL DESIGN AND ENDPOINTS

This is an operationally seamless Phase 2/3, randomized, placebo-controlled, multicenter trial to evaluate the safety, immunogenicity, and efficacy of INO-4800, administered by ID injection followed immediately by EP using the CELLECTRA[®] 2000 device, in a 2-dose regimen (Days 0 and 28) in adults who are at high risk of SARS-CoV-2 exposure. Subjects 18 years of age and older are expected to be enrolled across two (2) segments of this study. In the Phase 2 segment, approximately 400 seronegative subjects will be enrolled. In the Phase 3 segment, approximately 6714 seronegative subjects are expected to be enrolled, and 402 seropositive subjects will be enrolled. The subjects and data from Phase 2 are independent from that of Phase 3. The primary objectives of this trial are to identify in seronegative subjects an optimal age-related dose (Phase 2 segment) for subsequent evaluation for efficacy (Phase 3 segment).

Phase 2 Segment – Dose Selection

In the Phase 2 segment, approximately 400 subjects 18 years of age and older will be evaluated across four (4) dose groups (Table 1, Figure 1). Subjects will be randomized at a 3:3:1:1 ratio to receive either 1.0 mg or 2.0 mg of active investigational product (INO-4800) or 1 or 2 injections of placebo (placebo for INO-4800). Dose groups receiving INO-4800 will enroll approximately 150 subjects per group. Dose groups receiving placebo will enroll approximately 50 subjects per group. Randomization will be such that approximately 240 subjects aged 18-50 years, 120 subjects aged 51-64 years and 40 subjects aged \geq 65 years will be enrolled. Initial enrollment will include subjects aged 18-50 years. Initiation of enrollment of older subjects 51-64 years of age and elderly subjects 65 years and older will depend on review of safety and immunogenicity data from those age groups generated in the Phase 1 study (COVID19-001).

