3.8 SAFETY ASSESSMENT

Subjects will be followed for safety during the trial through scheduled clinic visits and phone calls. AEs, regardless of relationship to study drug, will be collected from the time of consent until 28 days post-dose 2 (i.e., Day 56). SAEs, MAAEs and AESIs will be collected from time of consent until EOS. SAEs, AESIs, and treatment-related AEs will be followed to resolution or stabilization. For the Phase 2 segment and at selected sites in the Phase 3 segment, solicited local and systemic AEs will be collected for 7 days following each dose using a participant diary.

Subjects will also be monitored for COVID-19 disease.

Please refer to the Schedule of Events (Table 3 and Table 4) for safety assessments to be performed.

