Urine samples will be tested by dipstick for glucose, protein, and hematuria at Screening (Phase 2 segment only) and at visits specified in the Schedule of Events (Tables 3 and 4). If abnormal (presence of protein, hematuria, or glucose \geq 1+), a microscopic examination should be performed.

Serology:

HIV antibody or rapid test will be measured at Day 0 only.

Antibodies to SARS-CoV-2 will be measured at Screening and at visits specified in the Schedule of Events (Tables 3 and 4).

Pregnancy Testing:

Pregnancy testing will be performed on women of childbearing potential (WOCBP). All women will be assumed to be of childbearing potential unless they are:

- Women who are post-menopausal as defined by reported spontaneous amenorrhea for ≥ 12 months;
- Women who are surgically sterile or have a partner who is sterile (i.e., vasectomy in males or tubal ligation, absence of ovaries and/or uterus in females). In the case of a vasectomy, subjects should wait six (6) months post-vasectomy to be considered sterile.

Phase 2: For WOCBP, a serum pregnancy test will be obtained at Screening and a urine pregnancy test will be performed immediately prior to any dosing and at the subject's last visit.

Phase 3: For WOCBP, a urine pregnancy test will be obtained at Screening and will be performed immediately prior to any dosing.

A negative result for urine β -HCG (test must have a sensitivity of at least 25 mIU/mL) must be available prior to each administration of IP. If the β -HCG test is positive, indicating that the subject is pregnant prior to completing the specified dose regimen, then no further IP

INO-4800	COVID19-311
Inovio Pharmaceuticals, Inc.	Clinical Protocol

will be administered. Every attempt should be made to follow pregnant subjects for the remainder of the study and to determine the outcome of the pregnancy (see Section 7.12).

DIARY

Diaries will be implemented in the Phase 2 segment of the protocol and at selected sites (estimated to include 711 subjects) in the Phase 3 segment. Subjects will be provided a diary to record the following solicited local and systemic AEs:

- Oral temperature and time taken (each daily entry before 11:59 pm)
- Solicited systemic symptoms
- Solicited local injection site symptoms
- Concomitant medications

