6.4.4 ASSESSMENT OF CLINICAL TRIAL ADVERSE EVENTS (AES)

Subjects will be queried regarding the occurrence of any AEs including AEs related to injection site reactions, concomitant medications and new onset illness or disease during their study visits and phone calls. Subjects will be reminded to contact study personnel and immediately report any event for the duration of the study. All AEs will be captured from the time of the informed consent until 28 days post-dose 2 (Day 56). Following the Day 56 visit, only SAEs, AESIs and MAAEs will be collected. All related AEs, AESIs and SAEs will be followed to resolution or stabilization. These events will be recorded on the subject's CRF.

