8.4 ANALYTICAL POPULATIONS

Analysis populations will be:

The per-protocol (PP) population includes all subjects who receive all doses of Study Treatments and have no protocol violations. Subjects in the PP population will be grouped to treatment arms as randomized. Subjects excluded from the PP population will be identified and documented prior to unblinding of the trial database. Analyses on the PP population among those who are baseline SARS-CoV-2 seronegative will be primary for the analyses of efficacy in the Phase 3 segment of this trial.

The modified intention to treat (mITT) population includes all subjects who receive at least one dose of Study Treatment. Subjects in this population will be grouped to treatment arms as randomized. Analysis of the mITT population will be considered supportive for the corresponding PP population for the analyses of efficacy in the Phase 3 segment of this trial.

The intention to treat (ITT) population includes all subjects who are randomized. Subjects in this sample will be grouped to treatment arms as randomized. Analysis of the ITT population will be considered supportive for the corresponding PP population for the analyses of efficacy in the Phase 3 segment of this trial.

The safety analysis population includes all subjects who receive at least one dose of Study Treatment. Subjects will be analyzed according to the treatments received.

8.5 **DESCRIPTION OF STATISTICAL METHODS**

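### Phase 3 solicited reactions come from diaries at sites covering about 10% of subjects, but Section 8.5.3.1 summarises them over everyone dosed, so reactogenicity rates mix two ascertainment methods and are understated

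*Protocol*

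**What the plan says.** **Collection.** Section 3.8 says that, besides the Phase 2 segment, "at selected sites in the Phase 3 segment, solicited local and systemic AEs will be collected for 7 days following each dose" by participant diary. The diary text in Section 6.4 sizes this subset: diaries are used "at selected sites (estimated to include 711 subjects) in the Phase 3 segment". The diary runs from the evening of dosing through 6 days after it and prompts for a fixed list of systemic and injection-site symptoms. Entries of Grade 1 or higher are normally recorded as adverse events, so they reach the AE tables.

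**Denominator.** Section 8.5.3.1: "All AEs including injection-site reactions will be summarized among the Safety Population by frequency per treatment arm". Section 8.4: "The safety analysis population includes all subjects who receive at least one dose of Study Treatment". Section 8.4 defines no diary population. Section 8.5.3.1 plans 30-day, 7-day and any-time summaries and names no other denominator for any of them.

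**Endpoints.** Phase 3 secondary endpoints 1a and 1b (Table 7) are the incidence of solicited and unsolicited injection-site reactions and of solicited and unsolicited systemic AEs.

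**Window.** Section 8.5.3.1: "The main summary of safety data will be based on events occurring within 30 days of any dose". Section 6.4.4: "All AEs will be captured from the time of the informed consent until 28 days post-dose 2 (Day 56". After that, only SAEs, AESIs and MAAEs are collected.

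**Status.** Section 8.1 calls Section 8 the formal statistical analysis plan, so the denominator is stated here, not deferred.

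**The concern.** A solicited reaction rate is interpretable only over subjects who were actually asked, day by day, about that reaction. Here the numerator holds diary events from about a tenth of Phase 3 plus whatever a less structured query picks up from the rest, and the denominator is everyone dosed. The result is neither a solicited nor an unsolicited rate.

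What is at stake is the tolerability description of a vaccine given with a device. Absolute rates of pain, redness and pruritus, and the planned risk differences between arms, would come out too small. Phase 3 could also look better tolerated than Phase 2 merely because fewer of its subjects kept diaries.

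**Working it through.** **Inputs from the Protocol.** Section 3.0: "approximately 6714 seronegative subjects are expected to be enrolled, and 402 seropositive subjects will be enrolled", so Phase 3 totals 6714 + 402 = 7116. The diary subset is about 711 (Section 6.4 and the Table 4 footnotes). Allocation is 2:1 (Section 8.7).

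**The plan's own figure.** 711 / 7116 = 0.0999. A tenth of 7116 is 711.6, so 711 is a 10% subset.

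**What the other 7116 - 711 = 6405 subjects receive.** Section 6.4.4 has all subjects asked at visits and calls about AEs, including injection-site reactions, and Section 6.4.5 has all observed for 30 minutes after dosing. After dose 1, the first scheduled contact is the Day 14 call (±3 days, so Day 11 at the earliest). After dose 2 it is the Day 42 visit, at least 10 days after the Day 28 visit (Table 4 footnote). Both fall after the diary week has closed, so non-diary subjects answer from recall.

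**Formula.** Let f = 0.0999 be the diary share. Let c be the share of reactions recorded outside diary sites, relative to diary capture. Assume the same true rate at both kinds of site. Then

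reported rate / true rate = f + (1 - f) × c.

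The documents give no value for c, so it is an assumption and is varied over its whole range.

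| c | reported / true | understatement | true 30% shown as | true 20-point difference shown as |
|---|---|---|---|---|
| 0 | 0.100 | 10.0-fold | 3.0% | 2.0 points |
| 0.10 | 0.190 | 5.3-fold | 5.7% | 3.8 points |
| 0.25 | 0.325 | 3.1-fold | 9.7% | 6.5 points |
| 0.50 | 0.550 | 1.8-fold | 16.5% | 11.0 points |
| 0.75 | 0.775 | 1.3-fold | 23.2% | 15.5 points |
| 1 | 1.000 | none | 30.0% | 20.0 points |

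Worked row, c = 0.25: 0.0999 + 0.9001 × 0.25 = 0.325; 1 / 0.325 = 3.1; 0.30 × 0.325 = 9.7%; 20 × 0.325 = 6.5 points.

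The 30% and 20-point figures are illustrations. In the c = 0.25 row, a reaction well inside the very common class of Table 5 (10% or more) would be displayed below that class.

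**Between arms.** If f and c are equal in the two arms, both rates are multiplied by the same factor. The rate ratio is kept and the risk difference shrinks by that factor.

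**With a diary denominator.** The factor becomes 1. A 2:1 split gives about 711 × 2/3 = 474 INO-4800 and 711 / 3 = 237 placebo subjects.

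**Window.** The main summary runs 30 days after each dose, but all-AE collection stops 28 days after dose 2, leaving 30 - 28 = 2 days uncollected. If the Day 56 call is read as the cut-off, the allowed extremes are dose 2 on Day 31 and the call on Day 51. The window would then end on Day 61, leaving 61 - 51 = 10 of 30 days without general AE capture.

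**The case against.** The strongest reply is that subjects outside diary sites are not left to volunteer events. They are questioned about injection-site reactions at the Day 14 call and the Day 28 and Day 42 visits, and are watched after each dose. This stands, and it excludes two stronger readings.

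A reader might infer that diary data are pooled with purely spontaneous reports; Section 6.4.4 says otherwise. A reader might also take ten-fold as the expected size. In tables that pool solicited and unsolicited events, that needs nothing at all to be recorded among some 6405 questioned and observed subjects. It would be reached if diary-solicited events alone were counted over the Safety Population, but Section 8.5.3.1 describes no such table.

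It is also fair that Phase 2 gives undiluted diary-based rates for the Phase 3 dose and device (about 150 subjects on 2.0 mg and 50 on two-injection placebo) and that safety is reported by phase. Phase 3 is double-blind, so there is no evident reason for capture to differ by arm. The documents therefore do not support inferring that the rule favours one arm. These are secondary summaries without a formal hypothesis, and the section itself urges caution over the intervals.

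The window point is minor. SAEs, AESIs and MAAEs continue to be collected, the window after dose 1 is covered, and 7-day reactions are untouched. The 10-day figure stacks two extreme visit windows on one reading of an ambiguous cut-off.

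What the reply does not remove is the denominator. Active questioning after the reaction week narrows the understatement; only capture equal to a prompted daily diary would abolish it.

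**Conclusion.** The point holds as a denominator error in the stated rule. As written, Phase 3 rates for endpoints 1a and 1b, and the Miettinen-Nurminen risk differences built on them, combine two ascertainment methods and are too low. The size cannot be fixed from the documents: about 3.1- to 1.8-fold if relative capture outside diary sites is 25-50%, with limits of 10-fold at zero capture and no effect at full capture.

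This assumes equal true rates at diary and other sites, diary capture as the reference, and a diary subset near the estimated 711. Rate ratios are roughly preserved if capture is similar by arm; absolute rates and risk differences are not. Phase 2 rates, the primary endpoint and the data collected are unaffected.

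It should be fixed but does not block the trial. The 30-day versus 28-day mismatch is real and secondary. The wording is confirmed in the two USA protocol versions shown (1.0USA and 2.0USA). Only the closing pages of Version 7.0 are shown, so whether it keeps the rule cannot be checked.

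**What to change.** In Section 8.4, add a solicited-safety set: dosed subjects at diary sites with at least one diary entry. In Section 8.5.3.1, report Phase 3 solicited local and systemic events within 7 days of each dose, with their risk differences, over that set only. Keep the full Safety Population for unsolicited AEs, SAEs, MAAEs and AESIs.

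Align the main summary window with collection, most simply at 28 days after each dose, and state whether all-AE collection ends 28 days after dose 2 or at the Day 56 contact.

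The cost is wording and one extra denominator, with no new data, visits or subjects. Solicited rates will rest on about 474 versus 237 subjects, so their intervals will reflect those numbers. Make the change before Phase 3 is unblinded, so that the choice of denominator cannot be questioned.
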